7.7 Trial Drug Administration

AM0010 is provided as a sterile, single use prefilled syringe, with a clear solution formulated at a concentration of 4 mg/mL. A pharmacy guide will be provided, which contains details regarding packaging, labeling, storage, (re)ordering and administration of AM0010 as well as FDA approved labeling of pembrolizumab.

A trial-defined AM0010 and pembrolizumab treatment will begin on trial day 1. Patients on Arm 1 will dose AM0010 prior to initiation of pembrolizumab. Patients on Arm 1 will dose AM0010 according to their weight:

- ≤ 80 kg body weight = 0.8 mg
- >80 kg body weight = 1.6 mg

AM0010 dose recalculations are only required if a patient's body weight changed from ≤ 80 kg to >80 kg or vice versa. Change in body weight should be calculated based on change from baseline weight or last weight taken per protocol.

Patients will be trained to self-administer AM0010 and will self-administer the dose throughout the trial starting with the first dose. A patient's caregiver may also be trained to perform SQ injections. Both the patient's and caregiver's training must be recorded in the patient's medical records. The Investigator or a qualified designee must be present during administration of the first dose. An AM0010 administration diary must be kept for dosing compliance monitoring.

Pembrolizumab will be administered on Day 1 of each 21-day cycle;

- Patients on Arm 1 (including crossover patients) will be administered pembrolizumab at a fixed dose of 200mg over approximately 30 minutes IV infusion
- Patients on Arm 2 will be administered pembrolizumab at a fixed dose of 200mg over approximately 30 minutes IV infusion

Pembrolizumab should be obtained by each site as per routine institutional practice. For preparation and complete prescribing information, refer to the most current prescribing information in the region. Investigators or designees will review the patient's hematology and chemistry panels, liver function tests, and the incidence of hematologic and non-hematologic toxicities prior to and during immunotherapy regimens.

Medications used to treat pembrolizumab-related infusion reactions (eg, diphenhydramine, acetaminophen/paracetamol, corticosteroids) considered non-investigational medicinal products (NIMPs) and will not be provided by the sponsor. These will be obtained by the investigational sites as marketed product, which should be stored in accordance to the package insert.

7.8 Continued Treatment

7.8.1 Crossover

At the time of disease progression (as assessed by the Investigator) patients randomized to trial Arm 2 may crossover to study Arm 1 to receive AM0010 and pembrolizumab. When progressive disease is noted on the scan for an Arm 2 patient, no more than 21 days should pass before the patient crosses over to Arm 1. The scans and/or clinical assessment at crossover will be used as a new baseline to determine response or PD on Arm 1.

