	
 • Clinical evaluation: complete history, physical examination (Site/Organ System Status [includes: General appearance, skin, H/E/E/N/T – Thyroid, Pulmonary, Cardiovascular, Gastrointestinal, Musculoskeletal/Extremities, Genitourinary/Breast, Lymph Nodes, Neurological, and Psychiatric]), ECOG performance status, height, weight, vital signs, and documentation of concomitant medications. • Laboratory studies: hematology (WBC with differential, RBC count, reticulocyte count, and platelet count); aPTT and International Normalized Ratio (INR) or PT; comprehensive chemistry panel (sodium, potassium, chloride, CO₂, creatinine, calcium, BUN, albumin, AST, ALT, alkaline phosphatase, lactate dehydrogenase, and total bilirubin); Thyroid Function Test (TSH, free T3, and free T4); urinalysis with microscopic examination; and serum or urine pregnancy test for women of child bearing potential. • Pharmacokinetic: sparse sampling in all patients in Arm 1 and crossover and exploratory molecular biomarker sample collection in all patients. • Tumor Assessment: CT or MRI (if allergic to contrast media) scans will be performed every 9 weeks (± 7 days) during the study treatment and during the first year from discontinuation of the study treatment, every 12 weeks (± 7 days) during the second year, and every 16 weeks (± 7 days) thereafter, to evaluate response to treatment by RECIST v.1.1. • Tumor assessment will be repeated until disease progression, death, or receipt of new anti-cancer therapy, or until study completion, whichever is first, whether or not study treatment was administered • The same radiographic procedure to define measurable lesions must be used throughout the trial for each patient. • Patients will continue the assigned trial treatments until tumor progression by RECIST v.1.1 criteria (per Investigator's assessment) by CT or MRI (if allergic to contrast media), withdrawal from the trial, or intolerance of therapy not manageable with dose modifications outlined in the protocol/package insert and/or supportive care. Note: Patients with suspected radiographic pseudoprogression, in the absence of clinical deterioration, should remain on trial treatments and be rescanned at 4 weeks or later. If progression is confirmed on follow-up scan, patients in Arm 1 will be discontinued from the treatment and patients in Arm 2 may crossover to receive treatment with AM0010 with pembrolizumab if they fulfill eligibility requirements. Refer to Section 7.6. • Patients who discontinue trial treatments with response of CR, PR, or SD will undergo CT or MRI scan evaluations per protocol until time of PD or death, or until study completion or initiation of subsequent anti-cancer therapy, whichever is first. • Patients who demonstrate clinical progression will have a scan conducted at the time to document disease status by RECIST v.1.1. • The first scheduled tumor response assessment will be performed at 9 weeks (± 7 days), and responders (CR or PR per RECIST v1.1) will have a confirmatory scan at ≥ 4 weeks after response has been established using the same technique as baseline scans. • To mitigate the chance of detecting false progression (ie, pseudoprogression) early in the course of treatment with AM0010 in combination with pembrolizumab or the pembrolizumab-alone arm, patients whose scans show radiographic progression in the absence of clinical deterioration including worsening performance status as assessed by the Investigator may remain on trial treatments and an additional scan should be obtained at ≥ 4 weeks (± 7 days) as outlined in Section 7.6. If this subsequent scan shows disease progression, patients in Arm 1 will be discontinued from the treatment period of the trial; patients in Arm 2 may cross over to receive treatment with AM0010 in combination with pembrolizumab if they fulfil the necessary eligibility criteria. • All screening and on-trial CT/MRI scans for all patients randomized on the

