7.5 Tumor Assessments

- CT or MRI (if allergic to contrast media) scans will be performed every 9 weeks (± 7 days) during the study treatment and during the first year from discontinuation of the study treatment, every 12 weeks (± 7 days) during the second year, and every 16 weeks (± 7 days) thereafter to evaluate response to treatment by RECIST v.1.1.
- The same radiographic procedure (includes head, chest, abdomen, and pelvis) to define measurable lesions must be used throughout the trial for each patient.
- Patients will continue the assigned trial treatments until tumor progression (by RECIST v.1.1 criteria) by CT or MRI (if allergic to contrast media), withdrawal from the trial, or intolerance of therapy not manageable with dose modifications outlined in the protocol/package insert and/or supportive care. Note: Patients with suspected radiographic pseudoprogression, in the absence of clinical deterioration, should remain on trial treatments and be rescanned at 4 weeks or later. If progression is confirmed on follow-up scan, study treatments will be discontinued or patients on Arm 2 may be eligible for crossover. Refer to Section [7.6](#).
- Patients who discontinue trial treatments with response of CR, PR, or SD will undergo CT or MRI scan evaluations per protocol until time of PD, or death, or until study completion, or initiation of subsequent anti-cancer therapy, whichever is first.
- Patients who demonstrate clinical progression before their scans are due will have an unscheduled scan conducted to document disease status by RECIST v.1.1.
- The first scheduled tumor response assessment will be performed at 9 weeks (± 7 days), and responders (CR or PR per RECIST v1.1) will have a confirmatory scan at ≥ 4 weeks after response has been established using the same technique as baseline scans.
- All CT/MRI scans for all patients randomized on the trial will be collected prospectively and submitted to a central imaging vendor for archiving. These scans may be independently reviewed at a later time at the request of Lilly.

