7.6 Pseudoprogression and Confirmation of Disease Progression

Accumulating evidence indicates a minority of patients treated with immunotherapy may derive clinical benefit despite initial evidence of PD.

Patients will be permitted to continue treatment beyond initial RECIST 1.1 defined PD if they meet the following criteria:

- Investigator-assessed clinical benefit, and do not have rapid disease progression
- Continue to meet all other study protocol eligibility criteria
- Tolerance of study drug
- Stable performance status

Treatment beyond progression will not delay an imminent intervention to prevent serious complications of disease progression (eg, CNS metastases).

A radiographic assessment/scan should be performed 4 weeks (± 7 days) after original PD to determine whether there has been a decrease in tumor size, or continued PD. The assessment of clinical benefit should be balanced by clinical judgment as to whether the patient is clinically deteriorating and unlikely to receive any benefit from continued treatment with AM0010 and/or pembrolizumab. A confirmatory scan will be required in the case of clinical deterioration suspected to be disease progression.

For patients who continue AM0010 and/or pembrolizumab beyond initial progression, confirmed progression is defined as an additional 10% increase in tumor burden volume from the time of initial PD. This includes an increase in the sum of all target lesions and/or the development of new measurable lesions. Treatment beyond confirmed progression is not allowed.

When assessing disease progression, the Investigator should use a new baseline tumor burden that includes new lesions that developed at the time of initial progression. New lesions are considered measurable at the time of initial progression if the longest diameter is at least 10 mm (except for pathological lymph nodes which must have a short axis of at least 15 mm). Any new lesion considered non-measurable at the time of initial progression may become measurable and therefore included in the tumor burden volume if the longest diameter increases to at least 10 mm (except for pathological lymph nodes which must have a short axis of at least 15 mm).

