#### **6.5.5. Sensitivity Analyses**

##### **6.5.5.1. Progression Free Survival**

Progression-Free Survival Sensitivity Analysis 1 (PFS event is disease progression per scan or death): clinical progression will not be considered as a progression event.

Progression-Free Survival Sensitivity Analysis 2: (PFS event is the earlier of disease progression per scan, clinical progression, or death): pseudoprogression without confirmation is not considered as an event (progressive disease).

Progression-Free Survival Sensitivity Analysis 3 (PFS event is the earlier of disease progression per scan, clinical progression, death, or initiation of subsequent anti-cancer therapy): patient initiates subsequent anti-cancer therapy will be considered as a progression event at the date of initiation of subsequent anti-cancer therapy – 1 day.

Progression-Free Survival Sensitivity Analysis 4 (PFS event is disease progression per independently reviewed scan or death): clinical progression will not be considered as a progression event.

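### The protocol does not say which scan starts the 21-day crossover limit in Arm 2; counted from the first progression scan, it runs out before a qualifying pseudoprogression rescan.

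*Protocol*

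**What the plan says.** **Crossover.** Protocol 7.8.1 makes crossover optional at investigator-assessed progression: "patients randomized to trial Arm 2 may crossover to study Arm 1 to receive AM0010 and pembrolizumab". It then sets the time limit: "no more than 21 days should pass before the patient crosses over to Arm 1". The clock starts when PD is seen on the scan. The section does not mention confirmation and does not refer to Section 7.6. It also resets the baseline at crossover.

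**Rescan.** Section 7.5 says that patients with suspected pseudoprogression and no clinical deterioration "should remain on trial treatments and be rescanned at 4 weeks or later". Section 7.6 sets the time: "A radiographic assessment/scan should be performed 4 weeks (± 7 days) after original PD". Neither section excepts an arm.

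**Order of the two.** Section 7.5 continues: "If progression is confirmed on follow-up scan, study treatments will be discontinued or patients on Arm 2 may be eligible for crossover". The synopsis (Trial Procedures) likewise says that, once the later scan shows progression, "patients in Arm 2 may cross over to receive treatment with AM0010 in combination with pembrolizumab if they fulfil the necessary eligibility criteria". Section 3.0 contains both ideas. It allows Arm 2 crossover at investigator-documented progression without mentioning confirmation, and for suspected pseudoprogression it puts the crossover procedures after a confirming scan.

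**Analyses that use the rescan.** Protocol 10.2.1 bases response after suspected pseudoprogression on a CT scan at least 4 weeks later. The SAP admits responses beyond pseudoprogression in ORR4 (Section 6.5.2.3). In PFS sensitivity analysis 2 (Section 6.5.5.1), "pseudoprogression without confirmation is not considered as an event".

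**The concern.** A site that reads 7.8.1 alone will count 21 days from the first scan showing PD. A site that reads 7.5 or the synopsis will rescan first and cross the patient over afterwards. No section chooses between these, and the trial is open-label, so practice may differ between sites and with how keen a patient is to receive AM0010.

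Under the first reading, an Arm 2 patient with suspected pseudoprogression may have no later scan on pembrolizumab alone. Two analyses could then be distorted, in opposite directions:

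- **PFS sensitivity analysis 2.** The Arm 2 progression lacks confirmation and could be dropped as an event, while a similar Arm 1 progression is rescanned and counted. This makes Arm 2 look better and tilts against AM0010.
- **ORR4 and the protocol-defined ORR.** A late response on pembrolizumab alone cannot be seen in a patient who has already crossed over, while a late response in Arm 1 can. This tilts towards AM0010.

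**Working it through.** **Step 1: the two clocks, counted from the first PD scan.**

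| Rule | Source | Days |
|---|---|---|
| Crossover limit, Arm 2 | Protocol 7.8.1 | by day 21 |
| Rescan | Protocol 7.5 | day 28 or later |
| Rescan | Protocol 7.6 | 28 − 7 = 21 to 28 + 7 = 35 |
| Scan used for response after pseudoprogression | Protocol 10.2.1 | day 28 or later |

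The limit falls 28 − 21 = 7 days before the nominal rescan. With the 7.6 window, the two meet on day 21 only. A day-21 scan would still be 7 days too early for 10.2.1, so for the protocol's ORR rule there is no overlap.

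**Step 2: the same, counted from the confirmatory scan.** The rescan is already done when the 21 days begin, so nothing conflicts. The problem lies entirely in which scan starts the clock, and it concerns suspected pseudoprogression only.

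**Step 3: which analyses can be touched.**

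- Main PFS: Table JZGC.6.1 dates progression at the documented scan in both arms, whether or not it is confirmed. Not affected.
- SAP primary ORR (6.5.2.1): responses count only up to objectively documented progression. Largely unaffected; a loose pointer to protocol 7.6 keeps this from being absolute.
- PFS sensitivity analysis 2, ORR4 and the protocol 10.2.1 ORR: can be affected.

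**Step 4: illustration for PFS sensitivity analysis 2.** The documents give no pseudoprogression rate, so both rates here are assumptions. Let s be the share of first progressions called suspected pseudoprogression and c the share of those in Arm 2 that cross over without a rescan. Assume no true treatment effect, every PFS event a progression, all Arm 1 cases rescanned and confirmed, and unconfirmed Arm 2 progressions censored. The Arm 2 hazard is then multiplied by (1 − s·c), and the hazard ratio (HR, Arm 1 to Arm 2) is 1/(1 − s·c).

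| s | c | s·c | HR |
|---|---|---|---|
| 20% | 50% | 0.10 | 1/0.90 = 1.11 |
| 20% | 90% | 0.18 | 1/0.82 = 1.22 |
| 40% | 50% | 0.20 | 1/0.80 = 1.25 |
| 40% | 90% | 0.36 | 1/0.64 = 1.56 |

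A simulation (20,000 per arm, exponential PFS with median 10.3 months, assumed 18-month accrual, cut-off 12 months after the last patient) agrees when these patients are censored. Following them to a later progression instead gives lower values at the high rates, about 1.4 in the last row.

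**Step 5: illustration for ORR.** First the plan's own figure: 50 per arm, 45% against 70%, 1-sided 5%. Power = Φ{[Δ − 1.645·√(2p̄(1 − p̄)/n)] / √([p₁(1 − p₁) + p₂(1 − p₂)]/n)} = Φ{[0.25 − 1.645 × 0.0989]/0.0957} = 81.9%. The stated power above 80% reproduces.

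Now let both true rates be 45%, and let Arm 2 alone lose some late responses (assumed shares). The same formula gives the chance of a false positive:

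| Arm 2 loss (points) | Normal approximation | Exact binomial, unstratified test |
|---|---|---|
| 0 | 5.0% | 4.6% |
| 1 | 6.1% | 5.7% |
| 2 | 7.4% | 7.0% |
| 3 | 9.0% | 8.5% |
| 5 | 12.7% | 12.2% |

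These error rates bear on ORR4 and the protocol-defined ORR, not on the SAP primary analysis.

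**The case against.** The strongest reply is that the protocol already answers the question. Section 7.5 and the synopsis place Arm 2 crossover after the confirmatory scan when pseudoprogression is suspected. A specific rule would normally override the general one in 7.8.1, so the rescan is lost only at a site that overlooks those passages. This is a fair reading, and it rules out a stronger claim that a reader might infer: that Arm 2 is obliged to cross over within 21 days and so is denied a scan that Arm 1 receives. The documents do not support that. Crossover is permitted, not required; the limit is worded as a recommendation; and the rescan is planned for both arms. Nor are late responses visible in Arm 1 only, since Arm 2 patients who stay on pembrolizumab, or who cross over after the rescan, can show them too.

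Two further replies have partial force. Appendix A requires a baseline tumor assessment at crossover, and a day-21 scan would fall within the 7.6 window. But it would not satisfy 10.2.1, and 7.8.1 also accepts a clinical assessment as the new baseline. It can also be said that an investigator who crosses a patient over at the first scan has judged it true progression, so the PFS sensitivity rule would not drop it. That is plausible, but the SAP does not say how such a patient is classified.

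What stands is that 7.8.1 taken alone, and the crossover sentence in 3.0, do not mention confirmation, and that nothing states which scan starts the 21 days.

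**Conclusion.** The concern holds as an unresolved ambiguity with a limited statistical reach. If the 21 days run from the first PD scan, the limit expires 7 days before the nominal rescan and before any scan that meets 10.2.1. An Arm 2 patient who elects to cross over can then lose the confirmatory scan on assigned treatment, with no matching limit in Arm 1. If they run from the confirmatory scan, there is no problem.

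The reach is one sensitivity analysis of a secondary endpoint (against AM0010), plus ORR4 and the protocol-defined ORR (towards AM0010). It should not be read as a threat to main PFS. The SAP primary ORR is largely outside it.

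The size cannot be computed from the documents. The hazard ratios of 1.11 to 1.56 and the error rates of about 6% to 13% show only how the mechanism scales under assumed rates. The high unconfirmed-crossover shares also presuppose that many sites do not follow 7.5. The point is worth fixing because the two clocks are incompatible as written and the repair is cheap.

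**What to change.** **Protocol.** The synopsis and Sections 3.0, 7.5, 7.6, 7.8.1 and 10.2.1 must be reconciled, so that the scan that starts the 21 days is explicit and compatible with the rescan. No view is offered here on which clinical rule is right.

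**SAP.** For PFS sensitivity analysis 2, add one sentence that applies to both arms: a patient whose first PD is not followed by a rescan on assigned treatment, because of crossover, treatment discontinuation or new anti-cancer therapy, is counted as progressed at the first PD date. A rule for Arm 2 crossovers only would not do, since Arm 1 patients who stop without a rescan would stay uncounted and a new imbalance could follow.

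**Cost.** One phrase in the protocol and one sentence in the SAP. The downside is that a few unconfirmed progressions that were really pseudoprogression will count as events, possibly more of them in Arm 2 if crossover is the main reason for a missing rescan. The SAP sentence does not repair ORR4 or the protocol-defined ORR, because no counting rule recovers a response that was never observed. Those depend on the protocol change.

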7.9 End of Treatment Visit

Twenty-eight (28) days (± 7 days) after the last dose of trial treatment, patients are expected to return to the trial site to complete all end of treatment assessments as follows:

- Physical (including pregnancy results, Site/Organ System Status [includes: General appearance, skin, H/E/E/N/T – Thyroid, Pulmonary, Cardiovascular, Gastrointestinal, Musculoskeletal/ Extremities, Genitourinary/Breast, Lymph Nodes, Neurological and Psychiatric]), including weight

- Vital signs (5-minute sitting blood pressure, pulse, respiratory rate, oral temperature)
- 12-lead ECG
- Activated partial thromboplastin (aPTT) and International Normalized Ratio (INR) or Prothrombin (PT)
- ECOG performance status assessment
- Clinical laboratory tests (hematology, chemistry panel, thyroid function, and urinalysis)
- Biomarker blood sample
- Pregnancy test (urine or serum) in women of childbearing potential
- Concomitant medications
- Adverse events

7.10 Follow-Up Period

During the extended safety observation period, all randomized patients will be followed for safety 60 and 90 days (± 7 days) after the last dose of study treatment and monitored according to the SOA ([Appendix A](#)).

During the long-term follow-up period, all randomized patients will be followed for OS every 9 weeks (± 7 days) during the first year from the 90-day follow-up visit, every 12 weeks (± 7 days) during the second year, and every 16 weeks (± 7 days) thereafter. The survival follow-up will be conducted until death or study completion, whichever is first, whether or not trial treatment was administered.

For patients who were randomized, but withdrew consent, survival (date of death) will be obtained by use of publicly available information.

The Investigator (or designee) will acquire the following information from patients who were randomized:

- Tumor assessment will be repeated every 9 weeks (± 7 days) during the study treatment and during the first year from discontinuation of the study treatment, every 12 weeks (± 7 days) during the second year, and every 16 weeks (± 7 days) thereafter. Tumor assessment will be repeated until study completion, disease progression, death, or receipt of new anti-cancer therapy for patients who were randomized, and not treated or discontinue treatment before disease progression, and do not withdraw consent.
- Subsequent cancer treatments (all randomized patients).
- Any SAEs considered to be related to trial treatment, follow until resolution.
- Date and cause of death (all randomized patients).

